3.1 Primary objectives

Currently, drugs' efficacy in ADPKD has been evaluated by means of eGFR and TKV variations. In ADPKD, kidney function may remain preserved until the 4th to 6th decade of life, when advanced renal cystic involvement has occurred. In fact, measured GFR is a poor marker of disease severity and progression, especially in early phases, when it is preserved through compensatory hyperfiltration during a prolonged period (typically decades), but eventually declines sharply. Despite this, to date, eGFR remains the standard to assess kidney function in randomized clinical trials in ADPKD. By contrast, TKV in relation to age can identify patients with progressive disease. TKV is an accurate estimate of kidney cyst burden and associates with pain, hypertension, gross hematuria, proteinuria or albuminuria, and loss of kidney function. TKV increases exponentially in virtually every ADPKD patient, with an average of 5–6%/year in adults. Elevated TKV, particularly when used together with age and kidney function, identifies individuals who are at higher risk for progression to ESRD. Precise measurement of TKV is necessary in clinical trials to assess the impact of therapeutic interventions over short periods of time and can be obtained by planimetry or stereology analysis of CT images.

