8.1.2 Secondary Endpoints

The key secondary endpoint is *the percent change from baseline in htTKV as measured by CT-scan at 24 months*. The use of htTKV as a surrogate biomarker for progression of ADPKD is supported by the Consortium for Radiologic Imaging Study of Polycystic Kidney Disease (CRISP) which showed that baseline TKV strongly predicts subsequent loss of GFR. TKV is now widely used in RCTs for ADPKD.

Other secondary efficacy end-points include:

- Difference in rate of albuminuria change;

- Difference in rate of urological events and of hypertension onset (for not hypertensive patients at baseline);
- Hypertension worsening or amelioration (for those who are hypertensive);
- Exploratory efficacy Outcomes (changes from baseline in urinary EGF and EGF/MCP-1 levels).

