9. VISITS

9.1 Trial Procedures

9.1.1 Screening:

After written informed consent has been signed, assessments during the screening visits will include:

1) Confirm diagnosis and determine whether the subject meets inclusion and exclusion criteria and record demographic information;

- 2) Perform physical examination, including post-void body weight and height (first visit);
- 3) Record medical/PKD history (all visits);

4) Record concomitant medications and ensure subject's treatment meets current standard of care including lifestyle and dietary recommendations, especially for ingestion of at least
2-3 liters of fluid per day as appropriate, unless otherwise directed by study doctor (all visits);

5) Assess AEs, if reported (all visits);

6) Assess vital signs (include heart rate and blood pressure) (all visits);

7) Serum pregnancy test for WOCBP (1st visit);

8) Collect urine and blood samples for clinical laboratory analyses, including serum creatinine, liver function tests, glucose metabolism parameter, CBC and venous gas analysis (1st, 2nd visit);

9) Non contrast enhanced CT-scan of the kidneys for TKV measurement (3rd visit, once eligibility has been confirmed). In case a patient has undergone kidney CT- or MRI-scan in order to measure TKV within 6 months before randomization, basal CT scan for TKV measurement may be not undertaken).

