9.1.4 Treatment Period

Assessment at each on-treatment visit will include:

1) Perform physical examination, including post-void body weight and height;

2) Record medical/PKD history;

3) Record concomitant medications and ensure subject's treatment meets current standard of care including lifestyle and dietary recommendations, especially for ingestion of at least2-3 liters of fluid per day as appropriate, unless otherwise directed by study doctor;

4) Assess AEs, if reported;

5) Assess vital signs (include heart rate and blood pressure);

6) Serum pregnancy test for WOCBP;

7) Collect urine and blood samples for clinical laboratory analyses, including serum creatinine, liver function tests, glucose metabolism parameter, CBC and venous gas analysis;

8) IMP dispensation;

9) IMP reconciliation (subjects must return any unused IMP);

10) Non contrast enhanced CT-scan of the kidneys for TKV measurement (at the end of month 24).

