9.1.6.2 TKV measurement

Abdomen-pelvis CT-scan will be performed by using a 320-row multi detector device and the following acquisition parameters will be used: slice thickness 0.5 mm, increment 0.5 mm, rotation time 0.5 s; 120/200 kVp/mAs.

An automatic dose modulation system will be used in all cases. Images will be acquired without intravenous injection of iodinate contrast material. Scans will be performed from the diaphragm to the pubic symphysis.

CT data will be centrally transferred to and analysed on a workstation (HPXW8600), present within the DETO equipped with software dedicated to image reconstruction (Vitrea FX 2.1, Vital Images, Minneapolis, MN, USA). For each patient, Multi-planar Reconstructions (MPR) on the axial, coronal and sagittal planes and Volume Rendering

(VR) images will be used in order to assess renal parenchyma. A radiologist with more than 10-year experience in the field of abdominal CT will manually trace both kidneys (renal parenchyma and all cysts including exophytic cysts), excluding the renal pelvis and other hilar vascular structures. The semi-automatic 3D Analysis software will be used in order to quantify the TKV for each CT examination. All changes in TKV (delta TKV) will be calculated by analyzing any variation of absolute TKV values deriving from the different CT examinations.

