12.3 Statistical Methods

A comparative analysis for the primary outcome will be carried out under the principle of "intention-to-treat" and including data from all subjects who are randomized. The efficacy and safety of compared interventions will be assessed. Trial data will be summarized by the calculation of means and standard deviations for normally distributed variables, medians and interquartile ranges for non-normally distributed variables, and frequency and percentage for categorical variables. Missing data will be ignored. The primary and secondary outcomes, namely the slope of the annualized eGFR and TKV will be analyzed using standard statistics including linear mixed-effects models. A P value <0.05 will be deemed significant.There are no plans for interim analyses.

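### The key secondary endpoint is percent change in htTKV, but Section 9.1.6.2 derives change from absolute volumes and Section 12.3 names no scale; an analysis in mL would miss the stated endpoint and be less precise

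*Combined protocol and SAP*

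**What the plan says.** Section 8.1.2, and the synopsis in Section 1 in the same terms, set the key secondary endpoint as "the percent change from baseline in htTKV as measured by CT-scan at 24 months".

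Section 9.1.6.2, after describing image acquisition and kidney tracing, closes with: "All changes in TKV (delta TKV) will be calculated by analyzing any variation of absolute TKV values deriving from the different CT examinations". It mentions no percentage, logarithm or height adjustment.

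Section 12.3 is the only analysis text. It covers the primary and secondary outcomes, "namely the slope of the annualized eGFR and TKV will be analyzed using standard statistics including linear mixed-effects models". It does not name htTKV, a scale, a baseline covariate or a random-effects structure. Section 3.2 states the aim of limiting TKV growth, again without a scale.

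Four further facts bear on the point:
- Section 3.1 states: "TKV increases exponentially in virtually every ADPKD patient, with an average of 5–6%/year in adults".
- Sections 5.2 and 5.3 contain no criterion on kidney size.
- Sections 9.1.1 and 9.1.4 and Figure 1 schedule two scans per patient, one at baseline and one at Month 24. A CT or MRI from the six months before randomization may replace the first.
- No variance, effect size, power or precision figure is given for TKV or htTKV.

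**The concern.** An analyst who follows 9.1.6.2 and 12.3 as written could compare the arms on change in mL. That is a different quantity from the endpoint in 8.1.2. If growth is proportional to size, two patients with the same growth rate but different kidney sizes show very different changes in mL. The arm difference in mL is then weighted towards patients with the largest kidneys, and variation in entry size is added to the error.

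The trial is open-label and the plan does not say which scale prevails. Percent, absolute and modelled results can disagree, and the choice could be made with treatment-labelled data in view. Section 3.1 treats TKV as a better marker of early progression than GFR, so this endpoint is likely to carry weight in interpretation.

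**Working it through.** **1. There is no figure of the plan's own to reproduce.** The sample size of 150 is justified only for eGFR slope.

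**2. What proportional growth means in mL.** Months last 28 days (Section 7.1), so 24 months = 672 days. Month 24 counts from Day 0 and Section 4.1 places the baseline scan on Day -30, so the scan interval is about 702 days = 702/365.25 = 1.92 years. Take 5.5% per year, the middle of the range in Section 3.1, as a continuous rate:

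- Growth = exp(0.055 × 1.92) − 1 ≈ 11.1%.
- A 600 mL TKV gains about 67 mL and a 3000 mL TKV gains about 334 mL, at the same growth rate. (The two volumes are illustrations.)
- Counting 672 days only, growth is 10.6%, or 64 and 319 mL.
- With a baseline scan six months (about 183 days) before a Day -30 randomization, the interval is 672 + 30 + 183 = 885 days = 2.42 years, and growth is exp(0.055 × 2.42) − 1 ≈ 14.3%.

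**3. Height is not the problem.** With constant adult height h, (V24/h − V0/h)/(V0/h) = (V24 − V0)/V0. Percent change in htTKV and in TKV are the same number. The issue is relative against absolute scale.

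**4. Precision lost on the absolute scale.** Write absolute change as V0 × r, with baseline volume V0 (mean m, coefficient of variation c0) independent of relative change r (mean x, coefficient of variation cr).

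- Relative change: Var(r) = x²cr².
- Absolute change: Var(V0·r) = m²x²(c0² + cr² + c0²cr²). A treatment difference in r is multiplied by m.
- Efficiency of unadjusted absolute against relative change: cr²/(c0² + cr² + c0²cr²).
- After regression on baseline volume the residual variance is m²(1 + c0²)x²cr², so the efficiency is 1/(1 + c0²).

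Neither c0 nor cr is in the documents. Over assumed ranges c0 = 0.3-0.8 and cr = 0.4-1.25, selected results are:

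| c0 | cr | Loss, unadjusted | Loss, baseline-adjusted |
|---|---|---|---|
| 0.3 | 1.25 | 13% | 8% |
| 0.5 | 1.0 | 33% | 20% |
| 0.5 | 0.5 | 56% | 20% |
| 0.5 | 0.4 | 64% | 20% |
| 0.8 | 0.4 | 82% | 39% |

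For example, at c0 = cr = 0.5 the efficiency is 0.25/(0.25 + 0.25 + 0.0625) = 0.44, a loss of 56%. Adjusted, it is 1/1.25 = 0.80, a loss of 20%.

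**5. Simulation check.** Exponential growth was simulated over 672 days with 400,000 patients per arm. Assumed inputs were 25% slower growth in one arm, c0 = 0.4-0.7, growth SD 2-5 points per year, measurement error 2-4%, and size-growth correlation 0 or 0.3. Relative to the log ratio:

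- percent change loses 0-1%;
- unadjusted absolute change loses 19-77%;
- baseline-adjusted absolute change loses 10-35%.

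One case at 75 per arm (c0 = 0.5, growth SD 2 points per year, 2% error, no correlation) gives power of 91% for the log ratio, 91% for percent change, 64% for unadjusted absolute change and 84% for baseline-adjusted absolute change.

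**6. Two scans and a random slope.** At a common interval, two scans supply two variances and one covariance, which is three second moments. A random intercept and slope with their covariance plus residual error has four variance parameters, so it is not identifiable. Unequal scan intervals would separate the parameters only through the assumed form of growth over time.

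**The case against.** The strongest reply is that the endpoint is already defined, twice, as a percent change, and that nothing in 9.1.6.2 overrides it. That section describes measurement. Its last sentence may mean only that change is derived from the measured volumes, as any percent change must be. On this reading no one has prescribed an inferential analysis in mL. This is a fair reading, and a reader who infers that the protocol commits to analysing mL goes beyond the text. But the sentence covers every TKV change, gives the result its own name and calls the values absolute, and Section 12.3 does not bring the analysis back to percent or htTKV. The conflict in wording stands.

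A reader might also infer that the plan requires a slope model that cannot be fitted. The documents do not say so. In 12.3 the word slope may attach to eGFR alone, mixed models are named as one option among standard methods, and no random slope for TKV is specified. A two-visit repeated-measures model can be fitted to two scans, and it keeps patients who have only one. The identifiability point therefore applies to one model, not to mixed models in general.

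Finally, the precision figures rest on assumed coefficients of variation. That stands, which is why they are given only as ranges.

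**Conclusion.** The point holds as an inconsistency between the stated endpoint and the stated derivation and analysis. Under the protocol's own premise of exponential growth, and with no limit on entry kidney size, an analysis in mL would answer a different question and do so less precisely.

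The size is conditional: roughly 20-75% of the information if unadjusted and 10-35% if adjusted for baseline TKV. The simplest closed-form cases reach slightly beyond both ranges. It is tempting to state a fixed loss, such as a third to two thirds. That figure needs a baseline coefficient of variation near 0.5, a coefficient of variation of growth of about 0.4-1.0 and no baseline adjustment, and the documents supply none of these. The direction of the loss follows from Section 3.1 together with spread in baseline size; its amount does not.

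This is a secondary endpoint and the remedy is textual. The change should be made, but the point does not touch the primary analysis.

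**What to change.** Make 9.1.6.2 and 12.3 match 8.1.2:

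- **Outcome and model.** Analyse log(htTKV at Month 24 / htTKV at baseline) by arm with log baseline htTKV as covariate (ANCOVA). Alternatively, use a two-visit repeated-measures model on log htTKV. Name one of the two in advance.
- **Reported effect.** Back-transform to the between-arm ratio of growth factors (Month 24/baseline) with its 95% CI, and give the geometric mean percent change in each arm. The ratio of growth factors is not a ratio of percent growth: growth of 10% against 8% gives 1.10/1.08 = 1.02, whereas 10/8 = 1.25.
- **Absolute change.** Keep delta TKV in mL as a descriptive summary only, and say so in 9.1.6.2.
- **Random effects.** State that no random intercept-plus-slope model with residual error will be fitted to TKV, because only two scans are planned. Other mixed models remain acceptable.

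The cost is a wording change in two sections. The scans, visits and patients stay the same.

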9.1.6.3 Polycystic Kidney Disease History and Outcomes Surveys

A short PKD history survey will be completed once during screening to capture information from the subject's recollection, and documented past medical history where available. The survey should be updated at each visit if new information regarding past history becomes available.

The PKD outcomes survey will collect information relevant to the medical, social and economic consequences of new and ongoing PKD-related morbidities. New clinically relevant information and specific questions about outcomes will be collected at the following visits: screening, end of run-in, and during the unblind randomized treatment period either monthly (over the phone or in person).

If a subject who has been randomized discontinues the use of IMP, PKD outcomes will be collected at the normally scheduled trial visits, or by telephone contact, to the date of the originally planned Month 12 visit, if the subject agrees.

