4.5 Unblind Treatment Period (Day 0 to Month 24)

Only subjects completing the IMP run-in period tolerating at least 45/15 mg of tolvaptan and 500/500 mg of metformin will be allowed upon entry to this unblind period.

In the metformin arm, during the treatment period visits will be scheduled every 3 months (each month has 28 days duration), within 3 days of the end of the trimester.

In tolvaptan treated patients, visits will be performed every month for the first 18 months, then every three months (each month has 28 days duration), within 3 days of the end of the month or the trimester (as prescribed by the additional monitoring requested by AIFA).

Beside the clinic visit and dispensing new bottles of IMP, subjects will have blood drawn on the last day of this period for efficacy and safety measures. The treatment duration of these subjects will be 24 months from the end of IMP run-in. Subjects not continuing in this trial will complete EoTx visit assessments and be followed for 7 days to assess any ongoing AEs.

From that point forward, every effort to maintain adherence and continuation of the subjects until the end of the trial should be undertaken. If continued tolerability becomes an issue, subjects may temporarily interrupt treatment as needed.

All subjects have the right to withdraw their consent from further participation in the trial at any time without prejudice.

Regardless of discontinuation of IMP, the subjects are expected to complete all monthly visits and assessments including the Month 24 visit.

4.6 Follow-up Period (up to Day +21 since Month 24 or End of Treatment)

Randomized subjects will enter the follow-up period after they complete the unblind, randomized treatment period, or after their EoTx visit, if they discontinued IMP. The follow-up period will be for 21 days in duration.

There will be no scheduled visits/assessments during the first week of the follow-up period. After the first week, 2 visits should be scheduled during the remaining 2 weeks of the follow-up period (between Day +8 and Day +21). The first visit should be scheduled on approximately Day +8, the second visit on approximately Day +21. These visits will be clinic visit.

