7. STUDY DURATION

7.1 Study Duration

The trial has a 36 months overall duration, that include a 9 months recruitment period.

7.1.1 Screening Period:

Has a 2 weeks duration, it is included in the 9 months recruitment period.

7.1.3 Treatment Period:

It has a 25 months duration. Each month lasts 28 days. It includes the 3 weeks titration period and the 1 week run-in period.

7.1.4 Post-Treatment Follow-up Period:

It lasts 21 days.

7.1.4 Total Study Duration:

About 3 years.

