11.2 Permanent Treatment Discontinuation

After randomization, a subject may stop treatment permanently before Month 24 for a variety of reasons. Treatment discontinuations may be initiated by a subject who is not satisfied with treatment or may become medically necessary due to AEs or other issues, as determined by the investigator. However, each investigator must comprehensively review the circumstances and offer the subject options for continued treatment to the degree possible.

A subject who permanently discontinues treatment will be recorded as an **IMP discontinuation** on the eCRF. The subject will then enter the follow-up period as though they had reached the Month 24 visit. During the first week of the follow-up period, no procedures will be done. During the last two weeks of the follow-up period, the subject will have a total of 2 samples collected.

After the follow-up period, the subject will continue with all assessments up to and including their scheduled Month 24 visit, but will not be required to complete follow- up beyond that visit.

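### The PKD outcomes survey ends at Month 12 for subjects who stop drug, contradicting the Month 24 follow-up set elsewhere; the urological-event endpoint may be affected

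*Combined protocol and SAP*

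**What the plan says.** Section 9.1.6.3 sets up a survey: "The PKD outcomes survey will collect information relevant to the medical, social and economic consequences of new and ongoing PKD-related morbidities". It is given at screening, at the end of run-in, and monthly (by telephone or in person) during the randomized treatment period. For a randomized subject who stops drug, collection continues at the usual visits or by telephone, with the subject's agreement, but only "to the date of the originally planned Month 12 visit".

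The trial runs longer than that. Section 4.5 states: "The treatment duration of these subjects will be 24 months from the end of IMP run-in". Section 7.1 adds: "Each month lasts 28 days".

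Other sections give a later end for the same subjects:

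- Section 4.5, on subjects who have stopped drug: "the subjects are expected to complete all monthly visits and assessments including the Month 24 visit".
- Section 11.2, on permanent discontinuation, once the three-week follow-up is over: "the subject will continue with all assessments up to and including their scheduled Month 24 visit".
- Section 10.2 (third paragraph), on subjects off drug but not withdrawn: vital status, adverse events, concomitant medications, ESRD status and laboratory data are gathered up to the scheduled close of the trial.

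Section 8.1.2 lists "Difference in rate of urological events and of hypertension onset" (onset in those not hypertensive at baseline) as a secondary efficacy endpoint. It does not say which record supplies the events. Section 12.3 disposes of missing data by ignoring them.

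**The concern.** A Month 12 limit has no evident purpose in a 24-month trial, and the protocol gives no reason for it. As written, how long a subject is surveyed depends on whether he or she is still on drug: to Month 24 if so, to Month 12 if not. Stopping drug happens after randomization, and the reasons for it differ by arm. Section 2.1 describes polyuria and liver monitoring with tolvaptan. Section 10.6 sets lactate rules for metformin, and section 11 gives the two drugs different eGFR thresholds for stopping.

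If urological events are counted from the survey, the arm with more stopping would have less second-year time in which an event could be recorded. The comparison of event rates would then partly reflect unequal ascertainment, and section 12.3 offers no remedy.

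**Working it through.** The plan states no figure that depends on this window, so there is none to reproduce. The check compares the windows and then sizes the gap.

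**1. The windows, for a subject off drug who has not withdrawn**

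- Survey (9.1.6.3): Month 12.
- All visits and assessments (4.5, 11.2): Month 24.
- Adverse events, ESRD status, laboratory data (10.2, third paragraph): scheduled end of trial.
- Adverse event reporting (10.1.9): 100 days after last dose, or 100/28 = 3.6 trial months.
- Adverse event follow-up (10.2, first paragraph): 21 days after last dose.

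The survey rule therefore contradicts 4.5 and 11.2 and does not fit the third paragraph of 10.2. The adverse event windows also disagree with one another.

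**2. Size of the survey gap**

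- Treatment period: 24 × 28 = 672 days.
- Survey window for subjects off drug: 12 × 28 = 336 days.
- Gap: 672 − 336 = 336 days, and 336/672 = 50%.

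**3. Loss per subject**

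For a subject stopping at month t, survey months lost = 24 − max(t, 12).

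- t = 6: 24 − 12 = 12 lost, of 18 remaining.
- t = 18: 24 − 18 = 6 lost, of 6 remaining.

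Anyone who stops after Month 12 therefore has no survey data after stopping.

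**4. Average loss (assumption: stopping times uniform over 24 months)**

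- Half stop before Month 12 and lose 12 months each. The other half stop later and lose 6 on average.
- Mean loss = (12 + 6)/2 = 9 months.
- Mean time remaining after stopping = 12 months, so 9/12 = 75% of it is outside the survey window.

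**5. Share of planned survey time (assumption: 5% to 30% stop; the protocol gives no rate)**

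Planned time = 150 × 24 = 3,600 patient-months. Share lost = D × 9/24, where D is the proportion stopping.

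- D = 5%: 67.5 months, 1.9%.
- D = 10%: 135 months, 3.8%.
- D = 20%: 270 months, 7.5%.
- D = 30%: 405 months, 11.3%.

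**6. Imbalance between arms (illustration only)**

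A subject stopping in year 1 loses 12/24 of the survey time. If 25% stopped in year 1 in one arm and 10% in the other (assumed), the loss would be 0.25 × 12/24 = 12.5% against 0.10 × 12/24 = 5%. This is survey time, not all event follow-up.

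**7. After the change**

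With a Month 24 limit, the survey time lost by rule is zero. No sample size, power or significance figure changes.

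**The case against.** The strongest reply is that the Month 12 limit applies to one survey and other routes stay open. Section 10.1 treats hypertension, renal pain, renal infection, nephrolithiasis and hematuria as adverse events that are also trial endpoints. Section 10.2 gathers adverse events to the end of the trial for subjects off drug. Section 9.1.4 has each visit record PKD history, adverse events and vital signs, and Figure 1 schedules blood pressure through Month 24. Section 8.1.2 never says that urological events come from the survey.

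Much of this stands. A reader might infer that discontinuers contribute no events in the second year. The documents do not support that, because hypertension onset can be read from visit blood pressures and the other events may be reported as adverse events. A reader might also infer that intention-to-treat is breached for these endpoints, but section 12.3 states that principle for the primary outcome only. Nor do differing reasons for stopping establish informative censoring. They make it possible, provided that sites apply 9.1.6.3 over 4.5 and 11.2 and the events are not captured elsewhere.

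The reply does not remove the problem. Section 9.1.6.3 is the specific instruction for the survey, and a site could reasonably prefer it to the general rules. Neither the visit list in 9.1.4 nor the Figure 1 grid has a survey line to override it. The adverse event route is not a secure substitute either: under 10.1.9, a subject stopping at Month 3 would leave adverse event reporting about 3.6 trial months later.

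**Conclusion.** Wrong as written: an internal inconsistency. The mismatch itself is certain: Month 12 in 9.1.6.3 against Month 24 in 4.5 and 11.2, a gap of 336 of 672 days.

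The consequence is conditional. Second-year survey data on subjects off drug are lost only if sites follow 9.1.6.3. The urological-event comparison is biased only if, in addition, that endpoint is drawn from the survey and stopping differs by arm. The 1.9% to 11.3% range rests on assumed stopping rates and uniform stopping times and measures survey time alone. It should not be read as a share of all events lost.

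Hypertension onset is less exposed. The primary eGFR slope and Month 24 htTKV are not limited by this rule.

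**What to change.** In section 9.1.6.3, change Month 12 to Month 24 so that it matches 4.5 and 11.2. In 8.1.2 or 12.3, state which record supplies urological events and which supplies hypertension onset, and say that both are analysed over all follow-up regardless of drug status. If adverse event records are the chosen source, the windows in 10.1.9 and 10.2 must be reconciled as well.

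The cost is a one-word correction, a clarifying sentence or two, and second-year survey contacts for subjects off drug. Those contacts can take place at visits that 4.5 and 11.2 already require, or by telephone as 9.1.6.3 allows. The change should be made before subjects off drug pass Month 12, because survey answers not collected then cannot be reliably recovered.
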